7 TRIAL PROCEDURES AND ASSESSMENTS

7.1 SCHEDULE OF ASSESSMENTS

Prior to performing any trial assessments that are not part of the patients' routine medical care, the Investigator will ensure that the patient has provided written informed consent. Date of informed consent signature must be recorded in the eCRF.

Visit 1, baseline (Investigator visit)

- Patients who fulfill all eligibility criteria and sign the ICF will be included in the study
- The following patient characteristics are recorded in the eCRF:
 - Age (years)
 - Sex
 - Education
 - Marital status and housing situation
 - Medical history
 - Concomitant medication
 - Working ability
- Questionnaires:
 - All study questionnaires except for the lifestyle questionnaire will be handed out and completed by the patient at the clinic at the time of the baseline visit.
 - After completion the patient will hand in the questionnaire to the nurse at the clinic who will check for completeness and send it to an external vendor for data entry.
 - Lifestyle questionnaire: For patients randomized to the MSP arm, a web based form will be filled out during the first study week (Arm 2).
- Randomization: The Investigator/nurse at the clinic will send patient details of the included patient to Health Solutions who will randomize the patient and provide support to the patient according to randomization.
- Lifestyle goal(s): Personal lifestyle goals will be defined and recorded in the health diary during the first study week (Arm 2).

Six months assessment

- At six months after study entry the patients in both arms will receive questionnaires from the external vendor (Health Solutions) to be filled in and sent back to the vendor.
- For patients randomized to the MSP arm the web based lifestyle questionnaire is completed.

Visit 2, month 12 (Study nurse visit)

- Before the 12 months visit, the patients in both arms will receive questionnaires from the external vendor to be filled in and sent back to the vendor before the visit at the clinic.
- For patients randomized to the MSP arm, the web based lifestyle questionnaire is completed before the visit.
- Working ability will be recorded in the eCRF.
- Adherence data will be downloaded from the RebiSmart device.
- Any adverse event will be recorded in the eCRF.
- Health care personnel satisfaction will be recorded in the eCRF once per site, at the 12 months visit for the last patient at the site.

7.1.1 Treatment Period

The study period for each patient is 12 months. Study visits and schedule of assessments are summarised in the table below.

VISIT	Baseline Visit 1 (Investigator)	6 month Assessment	12 month Visit 2 (Study nurse)
Clinical assessments			
Informed consent signature	X		
Patient characteristics ¹	X		
Working ability	X		X
Concomitant Medication	X		X
Questionnaires ²	X	X	X
Randomization	X ³		
Lifestyle Questionnaire ⁴	X	X	X
Lifestyle Goals ⁴	X		X
Patient satisfaction			X
HC Personnel satisfaction ⁵			X
Adherence to treatment			X
Adverse Events			X
End of Trial Information			X

1. Age, sex, education, marital status, housing situation and medical history
2. MSIS-29, EQ5D-5L, HADS, FSS, MFIS, and MUSIQoL selected questions
3. Performed by Health Solutions during first study week
4. For patients randomized to the MSP arm
5. Once per site, at the 12 months visit for the last patient at site

7.2 ASSESSMENT OF EFFICACY

Primary endpoint

MSIS-29 psychological scale (9 questions): Change from baseline to month 12.

Secondary endpoints

- MSIS-29 psychological scale (9 questions): Change from baseline to month 6
- MSIS-29, full scale: Change from baseline to months 6 and 12
- EQ5D-5L: Change from baseline to months 6 and 12
- Adherence: Proportion of patients with <10% missed injections during 6 and 12 months, measured with the software RDS 2.0
- FSS and MFIS: Change from baseline to months 6 and 12
- HADS: Change from baseline to months 6 and 12
- Working ability: Change from baseline to month 12 will be assessed by recording the following information per patient:
 - I am employed/have my own company
 - 1a. My employment is based on hours/week _____
I work my normal working hours (Y/N)
 - 1b. I now work hours/week _____
 - 1c. For the rest of the time I receive (sickness, activity compensation, parental compensation)
 - I study (indicate how much)
 - I have full sickness (full disability pension)
 - I have retirement
 - None of the above applies to me
- Adverse events: Proportion of patients with reported AEs at month 12
- Patients satisfaction:

The following question will be answered at the 12 months visit and recorded in the eCRF: "How satisfied are you with the overall treatment and support from health care providers during the last 12 months?"

Categorized as follows: Very unsatisfied / Unsatisfied / Satisfied / Very satisfied

Please specify: _____
- HC Personnel satisfaction:

The following question will be answered once per site at the 12 months visit for the last patient at the site and recorded in the eCRF: "How satisfied are you with the overall treatment and support from health care providers during the last 12 months?"

Categorized as follows: Very unsatisfied / Unsatisfied / Satisfied / Very satisfied

Please specify: _____

- Lifestyle questionnaire: Change from baseline to month 6 and 12 (arm 2)
- Lifestyle goals:
The following questions will be included in the questionnaires completed by the patients before the 12 months visit (arm 2):
 - Was the goal achieved? (Y/N)
 - If yes, better than expected or achieved as expected?
 - If better than expected, a lot or a little better than expected?
 - If no, a little or a lot less than expected?
- Health economy based on QoL and working ability at 12 months
- Questionnaires:
 - **MSIS-29** (Appendix II), a validated MS specific questionnaire consisting of 29 questions of which 20 address the physical impact component and nine assess the psychological impact. A combined score can be generated, or both components can be reported separately (25, 26).
 - **EQ5D-5L** (Appendix III), a standardized questionnaire to measure health and HRQoL, which can be used regardless of the patient's illness or treatment (27).
 - **HADS** (Appendix IV), to measure depression and anxiety in patients. The scale is limited to 14 questions, a practical tool for identifying and quantifying the two most common forms psychological disturbances in medical patients (28).
 - **FSS** (Appendix V), is a method of evaluating fatigue in multiple sclerosis and is designed to differentiate fatigue from clinical depression, since both share some of the same symptoms. FSS consists of answering 9 questions that require the subject to rate his or her own level of fatigue.
 - **MFIS** (Appendix VI) is a modified version of Fatigue Impact Scale (FIS) (29), based on items derived from interviews with MS patients concerning how fatigue impacts their lives. The instrument provides an assessment of the effects of fatigue in terms of physical, cognitive and psychosocial functioning. MFIS consists of 21 items.
 - **MUSIQoL** (Appendix VII), selected questions regarding memory and sex life.

7.3 ASSESSMENT OF SAFETY

7.3.1 Management and reporting of Adverse Events

Adverse events will be documented during the whole observational period, starting at the baseline visit, after signing of the informed consent form by the patient (both conditions must be met). Recording of adverse events stops when the Investigator signs off the eCRF at Month 12 or during an early discontinuation visit.

Definitions

Adverse Event:

An adverse event (AE) is any untoward medical occurrence in a patient or a clinical trial subject, administered a pharmaceutical product, which does not necessarily have a causal relationship with this treatment. An AE can therefore be any unfavorable and unintended sign (including an abnormal laboratory finding), symptom, or disease temporally associated with the use of a medicinal product, whether or not considered related to the medicinal product.

In cases of surgical or diagnostic procedures, the condition/illness leading to such a procedure is considered as the AE rather than the procedure itself.

In case of a fatality, the cause of death is considered as the AE, and the death is considered as its OUTCOME.

The Investigator is required to grade the severity/intensity of each adverse event.

Adverse Drug Reaction (ADR):

A response to a medicinal product which is noxious and unintended. Response in this context means that a causal relationship between a medicinal product and an adverse event is at least a reasonable possibility. Adverse reactions may arise from use of the product within or outside the terms of the marketing authorisation or from occupational exposure. Conditions of use outside the marketing authorisation include off-label use, overdose, misuse, abuse and medication errors.

Serious Adverse Event:

- Results in death.
- Is life-threatening at time of event.
- Requires in-patient hospitalization or prolongation of existing hospitalization.
- Results in persistent or significant disability/incapacity.
- Is a congenital anomaly/birth defect.
- Is otherwise considered as medically important.

Severity of an Adverse Event:

Investigators must assess the severity/intensity of Adverse Events according to the Qualitative Toxicity Scale, as follows:

Mild: The patient is aware of the event or symptom, but the event of symptom is easily tolerated.

Moderate: The patient experiences sufficient discomfort to interfere with or reduce his or her usual level of activity.

Severe: Significant impairment of functioning: the patient is unable to carry out usual activities.

Investigators must also systematically assess the causal relationship of AEs to Rebif using the following definitions. Decisive factors for the assessment of causal relationship of an AE to Rebif include, but may not be limited to, temporal relationship between the AE and Rebif, known side effects Rebif, medical history, concomitant medication, course of the underlying disease, trial procedures

- **Not related:** Not suspected to be reasonably related to Rebif. AE could not medically (pharmacologically/clinically) be attributed to Rebif under study in this clinical trial protocol. A reasonable alternative explanation must be available.
- **Related:** Suspected to be reasonably related to Rebif. AE could medically (pharmacologically/clinically) be attributed to Rebif under study in this clinical trial protocol.

7.3.2 Recording an Adverse Event

Each adverse event occurring during the study, whether serious or not, and whether common during MS treatment or not (such as flu-like symptoms), must be recorded in the eCRF, including its description, seriousness criteria, severity, duration (onset and resolution dates/times), relationship with the study treatment, actions taken (reduction/discontinuation of medication; other treatment or medication; other action) and outcome.

In addition, for all Serious Adverse Events, additional information must be completed and sent to the Sponsor (see next section).

7.3.3 Expedited Reporting of Adverse Events

The Investigator must notify the Sponsor WITHIN 24 HOURS of awareness of a new Adverse Event or of new information on a previously reported Adverse Event (= "follow-up").

To do so, the Investigator must complete the adverse event section of the eCRF.

If the event is non-serious an electronic notification will be sent to the Sponsor's Local Drug Safety department automatically, who will extract relevant data for reporting.

If the event is serious, the Investigator must also complete the Sponsor Serious Adverse Event Report Form/Fax template located in the eCRF, follow the eCRF's completion instructions, and fax it directly to the Sponsor's Local Drug Safety department. Reporting by e-mail is also possible.

[contact]

Email address: [contact]

For any new Adverse Event, the following minimum information is required as initial notification:

- Investigator name and contact details;
- Patient identification (study number, patient number, sex, age, ...);
- Merck Drug(s);
- Description of Adverse Event.
- Assessment of the causal relationship of AEs to Rebif

Note: the Fax template found in the eCRF is a standard form for reporting Serious Adverse Events. Its fields will not fully reflect all study designs and situations. Information should be provided based on what can be found in the eCRF (i.e., the RebiQoL protocol number + site number + patient number in the "patient ID" field, even if the number format does not perfectly match), as well as anything deemed important, rather than too strictly trying to follow the format of the reporting form.

When information is communicated via telephone, a written report must be sent immediately thereafter by fax or e-mail, again using the Fax template found in the eCRF. If some data are missing, the form has to be completed with the available data and a follow-up report must be sent as soon as possible.

The Investigator/Reporter must respond to any request for follow-up information or questions the Sponsor may have regarding the AE within the same timelines as for initial reports.

Serious Adverse Drug Reactions will be expedited by the Sponsor to Competent Health Authorities according to local regulations, which usually require a maximum period of 15 days. Non-serious Adverse Drug Reactions will be expedited by the Sponsor to Competent Authorities according to local regulations, which usually require a maximum period of 90 days.

Further to reporting Adverse Events to the Sponsor, the Investigator will comply with any local Pharmacovigilance requirements to report Adverse Reactions or SAEs to national Pharmacovigilance Systems (if applicable).

7.3.4 Pregnancy and In Utero Exposure

While not considered Adverse Events, all pregnancies occurring from the date of Informed Consent signature until four (4) weeks after the end of the observational study must be reported to the Sponsor's Global Drug Safety Officer, using the contact details found in the previous section. Active follow-up of all pregnancies should be performed, even if the patient was withdrawn from the study, as is usual practice. Investigators must actively follow-up, document and report to the Sponsor on the outcome of all these pregnancies. The Sponsor's Local Drug Safety unit might provide a special reporting form in case of a pregnancy.

7.3.5 Monitoring of Patients with Adverse Drug Reactions

Any AE that occurs during the course of a clinical trial and is considered related to Rebif®, and thereby classified as an Adverse Drug Reaction, must be monitored and followed up by the Investigator until stabilization or until the outcome is known, unless the patient is documented as “lost to follow-up”. This monitoring will be discontinued for non-serious ADRs at the time of database lock. Reasonable attempts to obtain this information must be made and documented. It is also the responsibility of the Investigator to ensure that any necessary additional therapeutic measures and follow-up procedures are performed.

8 Data Analysis and Statistics

Statistical analysis will be performed by an external vendor. A detailed description of all analysis will be presented in a separate Statistical Analysis Plan.

8.1 PREDETERMINATION OF SAMPLE SIZE

Assuming a group difference of 14 points (Arm 2 superior to Arm 1) and a standard deviation of 25 points on the primary endpoint a total of 104 patients are required for 80 % power and 5 % significance level with a randomization ratio of 1:1. In order to allow for a 20% drop-out rate 130 patients will be included.

8.2 RANDOMIZATION

The patients will be randomized to one of two arms (1:1):

Arm 1: Technical support for the RebiSmart device

Arm 2: Patient support program MSP

The randomization will be stratified for sex (M, F) and severity of disease (EDSS > 4.0 vs. ≤ 4.0 at baseline).

At visit 1 the Investigator/nurse at the clinic will send patient details of the included patient to Health Solutions who will randomize the patient based on 4 separate listings provided by the statistician;

- List 1: Female and mild disease
- List 2: Female and severe disease
- List 3: Male and mild disease
- List 4: Male and severe disease

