8.6.2 Analysis of Primary Endpoint

The primary endpoint will be analyzed using a linear mixed model with the change from baseline to month 6 and month 12 as dependent variable and group, time and baseline value of the dependent variable as fixed factors. The patient specific intercept will be included as a random factor. The difference between groups at month 6 and month 12 will be presented along with 95 % confidence intervals. The 12 month is the primary endpoint.

The derivation from the 9 questions to the MSIS-29 psychological scale can be performed using the following equation:

$$\text{Score (0-100)} = (\sum(9 \text{ questions}) - 9) / 0.36$$

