8.6.3 Analysis of Secondary Endpoints

Numeric secondary endpoints will be analyzed using the same method as for the primary endpoint. Dichotomized endpoints (e.g. proportion of patients meeting the criteria for adherence) will be analyzed at month 6 and month 12 separately using a logistic regression. The results will be presented as odds ratios with 95 % confidence intervals.

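### The stated linear mixed model leaves out sex and EDSS category, the two randomisation strata, so its standard errors are too large if either factor predicts change beyond the baseline score

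*Protocol*

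**What the plan says.** Section 8.2 sets up four randomisation lists, one for each combination of sex and disease severity: "The randomization will be stratified for sex (M, F) and severity of disease", the latter as EDSS above 4.0 versus 4.0 or below at baseline. Sections 5.3 and 6.2 repeat the stratification without the EDSS cut-off.

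Section 8.6.2, and the synopsis in the same terms, describes a linear mixed model for change in the MSIS-29 psychological score at months 6 and 12, with month 12 primary. Its fixed terms are "group, time and baseline value of the dependent variable as fixed factors". Its only random term is given by "The patient specific intercept will be included as a random factor". Neither stratification factor appears.

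Section 8.6.3 extends this model: "Numeric secondary endpoints will be analyzed using the same method as for the primary endpoint". Dichotomised endpoints "will be analyzed at month 6 and month 12 separately using a logistic regression", and no covariates are listed for them.

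The opening of Section 8 adds: "A detailed description of all analysis will be presented in a separate Statistical Analysis Plan".

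**The concern.** Stratified allocation keeps the arms balanced on sex and EDSS category. If these factors are related to the outcome, the balance lowers the true sampling variance of the treatment difference. A model without them leaves the variance they explain in the error and patient-intercept terms. It therefore reports a standard error for a trial without that balance. The result is a confidence interval that is too wide and a test whose type I error lies below the nominal 5%.

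What is at stake is the calibration of the primary result and of every numeric secondary result that uses the same model, together with some power that the design makes available at no extra cost.

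**Working it through.** **Inputs from Section 8.1.** Difference 14 points, SD 25 points, 5% significance, 80% power, 1:1 allocation, 104 patients, 130 after allowing for 20% drop-out.

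**The plan's own figure.** The two-sided normal formula gives n per arm = 2 × (1.960 + 0.842)² × 25² / 14² = 50.1, so 51 per arm and 102 in total. With the t distribution, power is 79.97% at 51 per arm and 80.7% at 52, so 52 per arm, or 104, reproduces the stated number. Then 104 / (1 − 0.20) = 130. The sample size is sound and does not depend on the strata.

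**Assumptions.** R² is the share of outcome variance, after the other model terms, that sex and EDSS category explain. The documents give no value, so a range that starts at zero is used. The SD of 25 is taken as the SD before the strata are added. The lists are assumed to balance the arms within each stratum; the protocol states no block size.

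**Formulas, with 52 per arm.**
- SE reported without the strata: 25 × √(2/52) = 4.90.
- SE with the strata: 4.90 × √(1 − R²).
- Excess width of the interval: 1/√(1 − R²) − 1.
- Actual type I error without the strata: 2 × [1 − Φ(1.96/√(1 − R²))].
- Power with the strata: Φ(14/SE with strata − 1.96).
- Power without the strata: Φ((14/4.90 − 1.96)/√(1 − R²)).

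Both power figures use the normal approximation, so they can be compared.

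| Assumed R² | SE with strata | Interval too wide by | Type I error without strata | Power with strata | Power without strata |
|---|---|---|---|---|---|
| 0% | 4.90 | 0% | 5.0% | 81.5% | 81.5% |
| 2% | 4.85 | 1.0% | 4.8% | 82.2% | 81.7% |
| 5% | 4.78 | 2.6% | 4.4% | 83.4% | 82.1% |
| 10% | 4.65 | 5.4% | 3.9% | 85.3% | 82.7% |
| 20% | 4.39 | 11.8% | 2.8% | 89.1% | 84.2% |

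**Check by simulation.** The month-12 comparison was simulated as a least-squares model with 104 patients and permuted blocks of 4 in the four strata, assuming 70% women and 15% with EDSS above 4.0. There were 6,000 trials per scenario. At R² = 10% and no treatment effect:
- Without the strata, the estimate had a true SD of 4.60, the mean reported SE was 4.89, and type I error was 3.8%.
- With the strata, the true SD was 4.58, the mean SE 4.64, and type I error 4.6%.

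With a true difference of 14 points, power was 81.9% without and 84.4% with the strata. At R² = 0 the two models gave practically the same results.

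**The case against.** **The model list may be only a summary.** Section 8.6.2 promises group differences at each time point yet lists no group-by-time term, and Section 8 defers detail to the SAP, which could add the strata. That is possible. But the section does name the model's terms, and a general deferral does not undo a stated list. An SAP that follows the list keeps the omission.

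**The loss is conditional and probably small.** This stands. If sex and EDSS predict nothing beyond the baseline score, nothing is lost. The top of the range is also demanding. Take the same assumed mix (30% men, 15% with EDSS above 4.0), SD 25, and R² split equally between the factors. The gap in change needed for one factor is then d = 25 × √((R²/2)/(p(1 − p))). A total R² of 5% needs about 11 points by EDSS and 9 by sex, 10% needs about 16 and 12, and 20% needs about 22 and 17. The whole assumed treatment effect is 14 points.

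**Two stronger readings are tempting.** A reader might infer that the estimate itself becomes less precise or that the trial is underpowered. Neither follows: in the simulation at R² = 10% the true SD is almost the same either way (4.60 and 4.58), and unadjusted power never falls below the stated 80% in the table.

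A reader might also extend the point to the logistic regressions. The protocol does not support this, because Section 8.6.3 lists no covariates for them, so they may properly be set in the SAP. The mechanism differs too. In a simulated example with log-odds coefficients of 1.2 in size for each factor and a treatment log odds ratio of 1.2, adding the strata raised the mean SE from 0.464 to 0.508. Power rose from 68.8% to 73.3%, mostly because the odds ratio was less attenuated.

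**Conclusion.** The point holds for the linear mixed model of the primary endpoint and for the numeric secondary endpoints that reuse it. The protocol stratifies on two factors and then lists a model without them. The consequence is one of calibration and forgone power, not of validity: there is no bias and no inflation of type I error.

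For R² between 0 and 10%, the interval is 0 to 5.4% too wide and the power forgone is 0 to about 2.6 percentage points (85.3 − 82.7). At 20%, which would need strong effects of both factors, the figures are 11.8% and about 5 points (89.1 − 84.2). These sizes rest on the assumed R² and on lists that balance the arms within strata.

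**What to change.** In Section 8.6.2 and the matching synopsis text, add sex and EDSS category (above 4.0 versus 4.0 or below, as used for randomisation) to the fixed factors, or state why they are left out. Section 8.6.3 then carries the change to the numeric secondary endpoints without further edits. Nothing need change in the protocol's logistic regression text on this account.

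The cost is one line in two places and two degrees of freedom. Both variables are already needed to randomise each patient, so no new data and no extra patients are required. If the factors turn out not to be prognostic, almost nothing is lost.

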2 SPONSOR, INVESTIGATORS AND TRIAL ADMINISTRATIVE STRUCTURE

Trial Sponsor: The principal Sponsor of this Phase IV, multicenter trial will be Merck AB, Solna, Sweden.

Location(s) of the Trial: This multicenter trial will be conducted in Sweden. It is estimated that 15-20 centres will participate in the trial.

Principal Investigator: The Principal Investigator (PI) will serve as the representative(s) for Investigators at each participating trial centre for decisions and discussions regarding this trial (ICH E6 GCP, 1.19). His/her/their role will be to provide expert medical input and advice relating to the trial design and conduct, and will be responsible for the review and sign-off of the Clinical Trial Report, on behalf of all participating Investigators.

For this trial, the contact information for the Principal Investigator will be entered on page 4 of this protocol.

Third-Party Service Providers: The Sponsor will rely on an external vendor (Health Solutions) for randomizing patients and providing appropriate support (technical or patient support program) according to randomization. They will also be responsible for sending questionnaires to patients at month 6 as well as for data entry of all questionnaires (baseline, 6 and 12 months).

The Sponsor will also rely on an external vendor for data management and statistics.

Monitoring: The sponsor will be responsible for site monitoring and site closure activities. The details will be described in a Monitoring Plan.

Drug Safety Responsibilities: The Sponsor's Safety department will be responsible for overseeing the safety of Rebif[®] during the conduct of this trial and will inform Health Authorities on all adverse drug reactions (ADRs) in compliance with existing regulatory requirements.

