5.3 CRITERIA FOR RANDOMIZATION

Once a patient has fulfilled all the inclusion and exclusion criteria and signed the ICF, the patient is included in the study. The investigator/nurse will send patient details of the included patient to Health Solutions who will randomize the patient and provide support according to randomization. The randomization will be stratified for sex and severity of disease.

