- An Introductory questionnaire which concerns different areas that affects health. The patient may also, in the questionnaire, indicate their willingness for change in each area (judging on a scale of 1 to 10).
- 6 motivating conversation with the personal health counselor.
 - The first conversation includes an initial analysis of individual needs and goal formulation based on the completed questionnaire. All patients will be offered stress management regardless of the result of the questionnaire as well as other support based on the analysis of individual needs.
 - The patients will formulate their own goals. The patient's goals and goal fulfillment are important in the process of change.
 - Five follow-up and motivating conversations will be distributed over a year.

3. Webb Support

The patient has access to two web-based personal health records, which can be adapted individually for optimal support:

- One managed by the personal nurse for coaching of treatment and understanding of the disease documented in a Health Record (“Hälsojournal” in Swedish)
- One managed by the personal health counsellor for coaching of life style documented in a Health Diary (“Hälsodagbok” in Swedish)

The information reported by the patient is used to provide individual feedback and to determine the content of the coaching conversations.

Health Solutions AB

MSP will be provided by Health Solutions AB, a registered healthcare company active in two areas; diagnosis-specific patient support and patient support for lifestyle changes. Health Solution AB is located in Luleå, Sweden.

The coaching includes several different communication alternatives; telephone, e-mail, outbound text messaging, online chats, as well as the technical platform RealQ supporting the personal health records. The patient can contact the personal coaches via telephone, instant messaging or e-mail according to his or her own needs. All calls are documented in the health records. In addition, all incoming mails to the personal nurse are documented in the patient's health record (“Hälsojournal” in Swedish).

The calls are performed according to the Motivating Interviewing (MI) method and are individually adjusted for the patients’ need. The calls are coordinated with mail and mobile text messaging.

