6.4 METHOD OF BLINDING

At visit 1, the patients will complete all questionnaires (except for the Lifestyle questionnaire), i.e. before allocation to study arm which will be performed by Health Solutions during the first week. The questionnaires will be sent for data entry to a unit within Health Solutions which is separate to the unit providing the patient support. At 6 and 12 months the questionnaires will be sent out directly to the patients for completion and the patients will return completed questionnaires to the separate unit at Health Solutions for data entry. The entered data will be transferred to an external vendor for data management and statistics. Thus, the Investigator/Study nurse will be blinded with respect to study arms unless the patient actively reveals it to the Investigator/Study nurse. In the patient information the patients will be asked not to reveal which study arm they are allocated to.

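### The company that delivers the tested support programme also assigns the arms, and the protocol neither separates the two tasks nor requires assignment in order of registration

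*Protocol*

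**What the plan says.** The protocol gives two tasks to one company. Section 2 names "an external vendor (Health Solutions) for randomizing patients and providing appropriate support (technical or patient support program) according to randomization". Section 6.1 confirms the delivery role: "MSP will be provided by Health Solutions AB, a registered healthcare company active in two areas".

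The order of events is in Section 5.3 and is repeated in Sections 7.1 and 8.2: "The investigator/nurse will send patient details of the included patient to Health Solutions who will randomize the patient and provide support according to randomization". Section 8.2 adds the tool, namely "Health Solutions who will randomize the patient based on 4 separate listings provided by the statistician". There is one list for each combination of sex and EDSS group.

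Section 6.4 gives the timing. Patients complete the baseline questionnaires "before allocation to study arm which will be performed by Health Solutions during the first week". It also describes one internal separation: "The questionnaires will be sent for data entry to a unit within Health Solutions which is separate to the unit providing the patient support".

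Section 2 plans a further party with no stated role in delivery: "The Sponsor will also rely on an external vendor for data management and statistics".

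**The concern.** Randomization protects the comparison only if nobody who knows both the patient and the next assignment can influence which patient gets it. Here the company that provides the programme receives the patient's details, works from the lists and has up to a week to assign. The protocol does not say that the coaching staff are kept away from the lists, that the next assignment is hidden until the patient is irrevocably registered, or that patients are assigned in order of arrival.

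This matters more than usual in this trial. Patients know their arm, the primary outcome is self-reported, and the programme is the sponsor's own service (Section 6.1). Unbiased allocation is therefore the main protection that the 12-month comparison has. If two patients in the same stratum were pending and the one thought more receptive to coaching went to MinSupport Plus, the comparison would tilt towards the programme. Adjusting for the baseline score (Section 8.6.2) would remove only the part of that tilt that the baseline score explains.

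**Working it through.** **Step 1. Who can see what before assignment**

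| Party | Before the arm is assigned | Source in the protocol |
|---|---|---|
| Enrolling site | Confirms eligibility, takes consent, collects baseline questionnaires; not shown to hold the lists | 5.3, 6.4, 7.1 |
| Health Solutions, data-entry unit | Receives baseline questionnaires; stated to be apart from the support unit | 6.4 |
| Health Solutions, otherwise | Receives patient details; works from the four lists; assigns within the first week; provides the support | 2, 5.3, 6.1, 6.4, 8.2 |
| Statistics and data-management vendor | Receives entered data; no delivery role stated | 2, 6.4 |

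The first row shows that sites cannot select on the arm. Section 5.3 places inclusion first: "Once a patient has fulfilled all the inclusion and exclusion criteria and signed the ICF, the patient is included in the study". The third row is the gap: no section states which unit holds the lists or makes the assignment.

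**Step 2. Could reordering be seen?**
The data for a check exist. The consent date goes into the eCRF (7.1), the investigator gives the patient number at inclusion (9.3), and the inclusion date is in the patient file (9.8). Comparing that order with the list order in each stratum would show reordering. Sections 9.7 and 9.10 mention quality control, monitoring and audits in general terms, but none is described as making this comparison.

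**Step 3. The plan's own figure**
Inputs from Section 8.1: difference 14, SD 25, 80% power, 5% level, 1:1. A two-sided t-test needs 51.03 per arm, so 52 per arm and 104 in total. Then 104 / (1 − 0.20) = 130. Both figures reproduce, and the fix changes neither.

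**Step 4. Illustration of size, on assumed inputs**
- Standard error with 52 per arm: SE = 25 × √(2/52) = 4.90 points.
- Assume that a fraction f of each arm is steered and that the steered patients differ by D points in expected change. The bias is b = f × D.
- Two-sided rejection probability under no true effect: P(Z > 1.96 − b/SE) + P(Z < −1.96 − b/SE).

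| f (assumed) | D (assumed) | b | Type I error |
|---|---|---|---|
| 0 | any | 0 | 5.0% |
| 10% | 12.5 | 1.25 | 5.7% |
| 10% | 25 | 2.5 | 8.0% |
| 20% | 25 | 5.0 | 17.5% |

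**Step 5. How plausible are those values of D?**
Take two pending patients with normally distributed outcomes and SD 25. Choosing the better one with a predictor that correlates r with outcome gains about (2/√π) × 25 × r = 28r points. D = 12.5 needs r = 12.5/28.2 = 0.44, and D = 25 needs r = 25/28.2 = 0.89. The second is implausible from patient details within a sex and EDSS stratum, so the two lower rows of the table are extremes.

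**Step 6. Opportunity**
130 patients over the one-year recruitment (5.1) is 130/52 = 2.5 per week, or about 0.6 per list per week if the strata were equal. A swap needs two patients pending in the same stratum, so the opportunities are limited but not absent.

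**The case against.** The strongest reply is that silence does not show a failure. Section 8.2 does not say that the lists are handed over complete or open. They could be sealed, loaded into a system or kept by a unit away from the coaches, under a procedure that is not part of the protocol. The vendor neither recruits nor judges eligibility. It needs only sex and EDSS to choose a list, and both are already stratified. Willingness to change is recorded in the lifestyle questionnaire, which only patients already in the programme arm complete (6.1, 7.1). The first calls also fall in week 1, which shortens the time for any reordering.

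Most of this stands, and it limits the point. Three stronger readings are tempting but unsupported:

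- A reader might infer that allocation concealment fails altogether. It does not: concealment from the enrolling sites is intact, and baseline scores are collected before the arm is known.
- A reader might infer that steering would leave no trace. Step 2 shows that the site records would reveal it if someone compared them with the lists.
- A reader might infer that the vendor also handles outcome data without any barrier. Section 6.4 states a barrier for data entry.

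The reply does not remove the core. The protocol itself gives assignment and delivery to one company, and it states an internal separation for data entry but none for allocation. A statistical analysis plan would not ordinarily change who holds the lists.

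**Conclusion.** The point holds in a limited form. The party that delivers the programme may have access to the sequence before it assigns each patient. The protocol requires neither assignment in order of registration nor a check of that order. Nothing in it suggests that any patient was or would be steered.

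The size of any bias is unknown and may be zero. The 1.25 to 5 point range rests wholly on assumed values of f and D and should not be quoted as an estimate. The conclusion assumes that no undisclosed vendor procedure already separates allocation from coaching. If one exists, the remaining task is to write it into the protocol. This is a cheap improvement, not an error that undermines the design.

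**What to change.** Change Sections 5.3, 7.1 and 8.2, with matching wording in the synopsis and Sections 2 and 6.4:

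1. The four lists stay with the independent statistics and data-management vendor.
2. The site registers patient number, sex and EDSS stratum with that vendor.
3. The vendor issues the arm in time-stamped order of registration, directly to Health Solutions and not visibly to site staff, so that the blinding in Section 6.4 is kept.
4. Health Solutions receives the contact details only together with the assigned arm.
5. Before database lock, all assignments are reconciled against the lists and the site-recorded inclusion order. This would also reveal any included patient who was never allocated. Such a patient would otherwise drop out of every analysis set in Section 8.5, since each starts from randomized patients.

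Minimum alternative: place the lists in a Health Solutions unit separate from the coaching staff, assign strictly in order of receipt, and carry out the same reconciliation.

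The cost is about 130 allocation messages, a short wording change and a short delay before the first call. The protocol does not say whether the statistics vendor can take allocation requests as they arrive, so that needs to be agreed with it. Sample size, visits, endpoints and analysis do not change.
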